Those that are randomised to shunt revision will have part or all of the shunt replaced. Patients randomised to the ETV arm of the study may have the malfunctioning shunt left in situ. Once the patient has had their surgery, they will be kept in hospital until they are deemed well enough for discharge home. There will be a visual assessment prior to discharge.

Follow-up will be arranged for 6 weeks, 6 months and one year for all study patients. At the 6 week and 6 month clinic the patient will have a cranial imaging to assess ventricular size. Those that have had an ETV will have an MRI scan to determine patency of the stoma as well (this is normal practice

following such a procedure). If a shunt revision is performed, a CT or MRI will be performed. Fundoscopy and visual acuity are also assessed in clinic. This is no different from the normal follow-up of a patient who has had treatment of a blocked shunt.

Should a patient make an unscheduled presentation because of symptoms related to their hydrocephalus or surgery and recurrence of the hydrocephalus is suspected they will be investigated in the usual manner in such cases (i.e. clinical and/or radiological confirmation of failure of shunt or ETV if that is the case).

A final proforma will be filled in at the patient's exit from the study. Exit from the study can happen in 3 ways:

- The patient represents with shunt/ETV failure
- The patient is well at one year following surgery with no need for further surgical intervention
- The patient voluntarily withdraws from the study for any reason at all

Duration of the study

Subject to R&D and ethics committee approval, enrolment into the study will commence on January 1st, 2007 and we would expect to enrol the 200th patient by December 31st, 2010. To ensure a minimum of one years-follow-up, data accrual will continue for one year after recruitment of the 200th patient. Overall we would expect this study to last at most 5 years.

Treatment efficacy assessment/endpoints:

In each patient the following endpoints will be assessed:

Primary endpoint:

One-year success rate of the procedure (one-year survival of shunt or ETV)

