- The procedure will be deemed a failure if the patient requires further surgical intervention within a year for treatment of their hydrocephalus. We felt that one-year follow-up was appropriate as most shunt and ETV failures occur in the first year following the procedure^{9,12}. The need for further surgery will be determined clinically or radiologically. In the case of patients who are in the ETV arm of the study, a sagittal MRI demonstrating the third ventricle floor will be sought where possible.

Secondary endpoints:

1. Occurrence of complications from surgery
2. Ventricular size changes
3. Length of inpatient stay
4. Number of re-attendances (excluding scheduled ones at 6 weeks, 3 months and 1 year) with symptoms related to their hydrocephalus/wound or implant.

Safety

Where either treatment would be deemed unsafe, the patient would be excluded from the study.

The risks of surgery are:

1. Death (less than 1% for shunt and ETV)
2. Epilepsy (approximately 5% short term risk in both treatments)
3. Minor vascular injury – Both treatments involve the passage of instruments through the brain to the ventricle. The risk of bleeding from this is about 5%. Most bleeds are sub clinical and don't result in neurological deficit. The risk of a bleed causing a deficit is about 1-2% for both treatments
4. Major vascular injury: This is a risk with ETV where basilar artery injury has occurred - death from it has been reported¹. However, most large series of patients treated with ETV, report no such injuries.
5. Infection: The shunt infection rate in this unit at present is 5%. The rate of CSF infection or ventriculitis is 0-10% in large series^{8,11,21} The rate of infection
6. CSF wound leak: This occurs in up to 5% of newly implanted shunt and is a high risk factor for infection. In the case of ETV it usually means that the ETV will not work and a shunt is needed²¹
7. Overdrainage and slit ventricle syndrome. This is a rare but serious problem in children treated with shunts. It can cause severe headaches and often requires further shunt surgery. It is not a recognised complication of ETV²²
8. Subdural haematomas. This is a complication seen with overdrainage of shunts in adults. It can mean that a patient will require surgery to remove the haematomas and shunt revision. It is also rarely seen with ETVs.

Subject withdrawal

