Obviously, a patient or family can withdraw from the study at any point. If they withdraw at any point before the one-year follow-up, they will be excluded from analysis at the end of the study.

Is endoscopic third ventriculostomy an effective treatment in patients with hydrocephalus and cerebrospinal fluid shunt malfunction?

Data recording and proformas

All data will be recorded prospectively on proformas by one of the investigators:

There will be a proforma for

- The initial inpatient admission, surgery and discharge
- Follow-up proforma to be filled in at one year or earlier if treatment fails

Data storage:

All proformas will be kept in paper form by the principle investigator in his office and will be transferred onto a computer database on one desktop PC in the department of neurosurgery. This will be password controlled and only the named investigators will have access to it

ETV vs. Shunt Revision Study: admission

Hospital number 1

Surname First name Date of birth Date of entry into study

Admission details

Date of admission
 
Mode of presentation
 
 Self referral
 
 Through OPD
 
 GP
 
 Other hospital
 
 A&E
 
 Other...
	
Cause of hydrocephalus
 
 IVH
 
 Aqueduct stenosis
 
 Myelomeningocele
 
 Chiari malformation
 
 Tumour
 
 CSF infection
 
 Head injury
 
 Dandy Walker
 
 Craniosynostosis
 
 Venous thrombosis
 
 Unknown
 
 Other

---	---

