- ventricle size decreased (still large)
- ventricle size unchanged (normal)
- ventricle size unchanged (still large)
- ventricle size increased
- Other...

MRI

- not done
- ventricle size decreased (normal)
- ventricle size decreased (still large)
- ventricle size unchanged (normal)
- ventricle size unchanged (still large)
- ventricle size increased
- flow through stoma (if ETV)
- Other...

Number of visits post discharge

Complications post-op	Free text
-----------------------	-----------

Status

- Functioning at one year
- Failed before one year
- Dead
- Lost to follow-up

Symptoms in successful patients

- none
- mild
- severe (requiring admissions)

Where failed: Date of failure

- Operation for failure
- shunt
 - ETV again
 - Other...

Cause of failure Free text

Statistical considerations:

The primary endpoints will be compared by a chi-squared test comparing success rates at one year in each group.

The timing of failure in those treatments that do fail will be compared using the Kaplan-Meier survival curves.

Complication rates are expected to be small and we expect no statistical difference in a study this size.

Mean numbers of reattendances and mean reduction in ventricular size will be compared using student's t-test

Data storage

All data will be stored on a PC and in paper form in the neurosurgical department.

Patients will be identified by their hospital numbers and only neurosurgical medical staff will have access to the data

Ethical considerations

There are no specific ethical issues in this study. Both treatments are well-recognised alternatives for managing patients with hydrocephalus

Publication of study findings

We plan to publish the results of this study in Journal of Neurosurgery

Presentations of the data will be made to at academic meetings (e.g. European Society for Pediatric neurosurgery and/or the International Society for Pediatric Neurosurgery)

2. Barlow P: Indications for endoscopic third ventriculostomy: a review of successful and failed cases. **British Journal of Neurosurgery** **11**:456, 1998

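### Re-attendances are compared as raw means although counting appears to stop at failure, so the comparison is confounded with the primary event

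*Protocol*

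**What the plan says.** Secondary endpoint 4 is "Number of re-attendances (excluding scheduled ones at 6 weeks, 3 months and 1 year) with symptoms related to their hydrocephalus/wound or implant". It is a count, with no time window and no denominator.

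The Study procedure section lists three ways out of the study. One is "The patient represents with shunt/ETV failure"; another is "The patient is well at one year following surgery with no need for further surgical intervention"; the third is withdrawal. It adds: "A final proforma will be filled in at the patient's exit from the study". The Data recording section has a "Follow-up proforma to be filled in at one year or earlier if treatment fails". That form holds one total, labelled "Number of visits post discharge", which does not separate unscheduled from scheduled visits.

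The Statistical considerations then give the analysis: "Mean numbers of reattendances and mean reduction in ventricular size will be compared using" Student's t-test. Time at risk is not mentioned.

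Two other statements bear on this. The Study procedure section arranges follow-up to one year for every study patient, which does not sit easily with exit at failure. The Subject withdrawal section drops patients who withdraw before one year from the analysis, so among those analysed failure is the main source of unequal follow-up.

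**The concern.** Read together, the exit rule and the timing of the form mean that a patient whose treatment works is observed for a year, and a patient whose treatment fails is observed only until it fails. Length of observation is then set by the primary outcome, and the t-test on raw means takes no account of it.

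Two effects follow, and they pull in different directions. Shorter observation lowers the count in patients who fail; someone who fails before first discharge cannot re-attend and scores zero. Against that, a patient who fails after discharge usually does so by re-presenting with symptoms, and the endpoint does not say whether that visit counts. If it does, each such failure adds one re-attendance that the primary endpoint has already recorded.

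At stake is the reading of the result. A difference in means would be taken as a difference in burden on patients, when it could arise with identical re-attendance rates in the two arms.

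**Working it through.** The Protocol gives no figure for re-attendances, so there is none to reproduce.

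**Inputs from the Protocol**
- One-year failure after shunt revision: 47/108 = 43.5%, so survival S = 0.565 (background text).
- One-year success of ETV in published series: 70%, so S = 0.70 (background text).
- 100 patients per arm (Randomisation process).

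**Assumed, because the Protocol gives nothing**
- A background re-attendance rate λ, equal in both arms, from 0.5 to 4 per patient-year.
- The distribution of failure times.
- Poisson counts, with time at risk started at surgery for simplicity.

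**Step 1. Patients with shortened counting.** 100 × 0.435 + 100 × 0.30 = 73.5, about 74 of 200.

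**Step 2. Expected count.** Mean = λ × E[min(T,1)] + c × (1 − S), where c = 1 if the failure visit counts and 0 if not. For exponential T, E[min(T,1)] = (1 − S)/(−ln S).
- S = 0.565: 0.435/0.571 = 0.762 patient-years.
- S = 0.70: 0.300/0.357 = 0.841 patient-years.

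The arm with more failures has about 9% less time at risk (0.762/0.841 = 0.906).

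**Step 3. Means at equal true rates (arm with 43.5% failing vs arm with 30% failing)**

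| λ per year | Failure visit not counted | Failure visit counted |
|---|---|---|
| 0.5 | 0.38 vs 0.42 | 0.82 vs 0.72 |
| 1 | 0.76 vs 0.84 | 1.20 vs 1.14 |
| 2 | 1.52 vs 1.68 | 1.96 vs 1.98 |
| 4 | 3.05 vs 3.36 | 3.48 vs 3.66 |

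If the failure visit is not counted, the arm with more failures always has the lower mean. If it is counted, the sign changes at λ = 0.135/(0.841 − 0.762) = 1.7. With failures spread evenly over the first month the change is at 0.135/(0.7125 − 0.5831) = 1.04; spread over the whole year, at 0.135/(0.85 − 0.7825) = 2.0.

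**Step 4. Rejection by the t-test, nominal 5%, failure visit not counted.** Simulating 4,000 trials of 100 per arm with exponential failure times gave 7.7%, 9.4%, 12.8% and 17.9% at λ = 0.5, 1, 2 and 4.

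**Step 5. Arms that differ only in failure timing.** Let 40% fail in each arm, at 1 month in one and at 6 months in the other, with λ = 1.
- Means: 0.60 + 0.40/12 = 0.633 and 0.60 + 0.40 × 0.5 = 0.800.
- Variance = mean + variance of time at risk: 0.633 + 0.24 × 0.917² = 0.835, and 0.800 + 0.24 × 0.5² = 0.860.
- Standard error of the difference: √((0.835 + 0.860)/100) = 0.130. Standardised difference: 0.167/0.130 = 1.28.
- Rejection is about P(Z > 1.96 − 1.28) = 25%, and simulation agrees.

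The figure is sensitive to the assumptions. Moving the early failures to 2 or 3 months gives 18% or 13%. Rates of 0.25, 0.5 and 2 per year give 10%, 16% and 40%.

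A gentler contrast has 43.5% failing in both arms, spread over the first 3 months in one and over the year in the other, with λ = 1. The means are 0.62 vs 0.78, or 1.05 vs 1.22 with the failure visit counted. When only timing differs, the earlier-failing arm is lower either way.

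**The case against.** **Truncation is inferred.** No sentence says that counting ends at failure, and the Study procedure section arranges one-year follow-up for every study patient. That is correct, and it is why the point is put as what the Protocol appears to do. But exit at failure, a form completed at failure and a single total on that form make truncation the natural reading. The Protocol fixes all three together with the test, so this is not merely detail deferred to an analysis plan.

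**The bias has no fixed sign.** A reader might infer that the arm that fails sooner or more often always gets the better-looking count. The documents do not support that. It holds if the arms differ only in timing, or if the failure visit is not counted. An arm with more failures can look worse if that visit counts and the background rate is below roughly 1 to 2 per patient-year.

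**Some of the difference may be real.** Setting 43.5% failing at 6 months against 30% failing at 1 month, with the failure visit counted and a rate of 1 per year, gives 1.22 vs 1.03 and rejection in about a third of trials. It is tempting to call all of that spurious, but 0.135 of the 0.193 gap (70%) is extra attendances that patients with failure really made. Without them the means are 0.78 vs 0.73 and rejection falls to 7% to 8%. That example shows overlap with the primary endpoint more than bias from time at risk, and it is not relied on here.

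**Counting to one year changes the question.** It would include attendances after a further operation, possibly the other procedure. This stands, and is a reason to offer it as an option with that consequence stated.

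**Conclusion.** The point holds as one of confounding, not of bias in a known direction. As written, the plan compares raw means over observation time that depends on the primary outcome, for about 74 of 200 patients at the quoted failure proportions.

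With equal true rates and the failure visit not counted, false rejection is about 8% to 18% at those proportions, and about 25% in one deliberately sharp contrast of failure timing. These sizes rest on assumed re-attendance rates and failure times that the Protocol does not supply, and on the inference that counting stops at exit.

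The endpoint is secondary. The chi-squared comparison of one-year success is unaffected. The change is worth making because the result is easily misread and the correction is cheap.

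**What to change.** 1. Reconcile exit at failure with one-year follow-up of all study patients, and state the counting window. The scheduled visits excluded in endpoint 4 (6 weeks, 3 months, 1 year) also differ from those in the Study procedure section (6 weeks, 6 months, one year) and must be reconciled, since they define what is unscheduled.
2. Report the failure presentation separately, because it is already the primary event.
3. Replace the t-test on raw means by one of two analyses:
   - A rate ratio (negative binomial, or Poisson with robust errors) with log time from discharge to failure or one year as offset. Patients who fail before first discharge have no time at risk; they should be reported as such and not scored zero. The ratio describes the rate while the treatment is still working.
   - A count of unscheduled related attendances to one year in every randomised patient, by allocated arm, whether or not treatment has failed. This also measures attendances after a further operation, and the report should say so.

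**Cost.** The first option is minor extra analysis; the discharge and failure dates are already on the proformas. The second needs a one-year record check for patients who failed, about 74 at the quoted proportions. Either way the follow-up form must separate unscheduled from scheduled visits.

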
Highest CRP
 
Highest WCC
	
ICP monitoring results
 
 not done
 
 inconclusive
 
 demonstrate shunt malfunction
	
Shunt tap
 
 not done
 
 unable to aspirate
 
 high pressure
 
 relieved symptoms
 
 demonstrated infection

---------------------------------------	---	---

Is endoscopic third ventriculostomy an effective treatment in patients with hydrocephalus and cerebrospinal fluid shunt malfunction?

ETV vs. Shunt Revision Study: discharge

Hospital number 1

Shunt xray not done migration
 normal Other...
 disconnection/fracture

CT scan not done
 enlarged temporal horns
 enlarged third ventricle
 enlarged frontal horns
 effacement of cortical sulci
 periventricular lucency
 increased ventricular size compared with baseline
 Enlarged 4th ventricle
 Aquaduct patent

MRI not done
 enlarged temporal horns
 enlarged third ventricle
 enlarged frontal horns
 effacement of cortical sulci
 periventricular lucency
 increased ventricular size compared with baseline
 Enlarged 4th ventricle
 Aquaduct patent

Surgery

Date of surgery

Findings Shunt infected (EVD intervening) Valve blocked
 Proximal block Overdrainage
 Distal block Other...

Procedure  Shunt revision
  Replacement of whole shunt  Replacement of proximal catheter  Replacement of distal catheter  Replacement of valve  Addition of ASD  Addition of reservoir	 ETV  ETV alone  ETV and EVD  ETV with VAD  ETV with lumbar drain  ETV and removal of original shunt  Other...
---	--

Complications

MRI prior to discharge not done
(in case of ETV) flow through stoma
 inconclusive
 no flow through stoma

Date of discharge

Is endoscopic third ventriculostomy an effective treatment in patients with hydrocephalus and cerebrospinal fluid shunt malfunction?

ETV vs. Shunt Revision Study: follow-up

Hospital number 1

Date of visit

CT during follow-up

- not done
- ventricle size decreased (normal)

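### The planned t-test on mean reduction in ventricular size does not fit the proformas, which record ventricular size only as tick-box categories with no named scan

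*Protocol*

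**What the plan says.** The second secondary endpoint is "Ventricular size changes", with no measure, unit or time point. Statistical considerations fixes its analysis: "mean reduction in ventricular size will be compared using student's t-test".

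On data capture, Data recording and proformas states: "All data will be recorded prospectively on proformas by one of the investigators". It lists two forms. One covers the admission, surgery and discharge. The other is described as "Follow-up proforma to be filled in at one year or earlier if treatment fails". Study procedure agrees: "A final proforma will be filled in at the patient's exit from the study".

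On imaging, Study procedure states: "At the 6 week and 6 month clinic the patient will have a cranial imaging to assess ventricular size". Routine cranial CT is also done before entry. No scan is scheduled at one year.

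**The concern.** A mean reduction needs a number for each patient: a size before surgery and a size afterwards, or a change score. The printed forms supply neither. An analyst holding the completed proformas would have to drop the stated test or invent scores for the boxes after seeing the data.

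Timing is a second gap. Ventricular size is imaged at two scheduled visits, but neither visit has its own form. The one follow-up form is completed at different times for patients who fail and patients who do not, and it does not identify the scan being described. A difference between arms could then mix a difference in ventricular size with a difference in when size was read.

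A statistical analysis plan could choose another test. The mismatch is nevertheless fixed in this document, because the protocol specifies both the test and the fields that are to feed it.

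**Working it through.** The protocol states no mean, standard deviation or target difference for ventricular size, so there is no figure to reproduce. The check sets the analysis against the forms.

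**1. What the test needs.** For patient *i*, reduction *d_i* = size before − size after. The t-test compares the arm means of *d_i*, using their standard deviations. It therefore needs a numeric *d_i* and a defined time for the second reading.

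**2. What the forms supply.**

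| Form and field | Content | Numeric size? |
|---|---|---|
| First proforma, CT and MRI (placed before the surgery block) | Tick-boxes for enlarged horns or ventricles, and for an increase over baseline | No |
| Follow-up proforma, CT and MRI | Five size boxes, plus a box for anything else | No |

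The five follow-up boxes run from "ventricle size decreased (normal") through decreased but still large, unchanged and normal, and "ventricle size unchanged (still large") to increased. The increased box carries no normal or still-large qualifier. The free-entry box is not a defined measurement.

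**3. Whether the boxes can stand in for a number.** An unscored category has no mean or standard deviation, and the protocol gives no scores. The five boxes also lack an obvious single order, because they combine direction of change with final state. Nothing says whether decreased but still large ranks better or worse than unchanged and normal. Collapsed to decreased / unchanged / increased, the order is clear, and a rank or ordinal comparison is possible.

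**4. Which scan is recorded.** The follow-up form has one visit date, one block of boxes per modality and no scan date. For a patient who succeeds, the tick could describe the 6-week or the 6-month scan. For a patient who fails, it could describe either of those, if already done, or a scan taken when failure was investigated. The form does not decide between them.

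**5. How many patients could have a failure-time reading.** The inputs are in the background section.

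- Shunt revision: 47 of 108 revisions in 2004 needed a further procedure; 47/108 = 43.5%, matching the stated one-year survival of 100 − 43.5 = 56.5%.
- ETV: a 70% success rate is cited from retrospective work; 100 − 70 = 30% failures.

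With the planned 100 patients per arm, that is at most about 44 (0.435 × 100 = 43.5) and 30 (0.30 × 100) patients. These are ceilings, for three reasons:

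- failure may be established clinically, without a new scan;
- patients failing after 6 months should already have both scheduled scans;
- nothing requires the failure-time scan to be the one ticked.

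**The case against.** The strongest reply is that little is lost. CT is routine before surgery, and all patients are to be imaged at 6 weeks and 6 months, so a ventricular measure could be read from existing images at any time. This stands as a limit on the point: what is missing is a recorded field and a definition, not the images. A reader might infer that the endpoint is beyond recovery, and the protocol does not support that. Scores of −1, 0 and +1 would also yield a computable mean. The protocol specifies no such scores, however, and the result would be a mean of ticks rather than a mean reduction in size.

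A reader might also infer that the arm with more failures must show larger ventricles simply because of when its forms are completed. The documents do not support this either. The form does not say that the failure-time scan is recorded, failure need not involve a scan, and larger ventricles after a failed procedure may be a genuine outcome. What remains is that undated readings at possibly different times prevent these explanations from being separated.

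Finally, this is one of four secondary endpoints, and no sample size rests on it. That is correct and limits the weight of the point.

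**Conclusion.** The point holds as an internal mismatch. The stated comparison of means cannot be computed from the data that the protocol says will be recorded, because ventricular size is captured only in categories, without a scoring rule or a reference time point. This rests on the printed forms being the complete data capture, which the protocol's own statement about proformas supports.

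The timing gap is a possibility, not a demonstrated bias. The 30% to 43.5% range is an upper limit on the share of each arm that could contribute a failure-time reading. It assumes that one unit's 2004 experience and a cited retrospective success rate carry over to this trial, and that the latter can be read as a one-year figure, which the protocol does not state. It says nothing about the size or direction of any bias.

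The plan should be corrected before enrolment, since the remedy lies partly in the forms. The primary chi-squared comparison of one-year success is unaffected.

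**What to change.** Name one scheduled scan, for example the 6-month scan, as the time point for this endpoint, and give the 6-week and 6-month readings their own dated lines on the follow-up form.

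State in advance how patients who fail before the named scan are handled. Failure ends study participation, so these patients may have no 6-month reading. Options are to analyse the 6-week scan as well, or to report failures separately. Substituting the last scan before reoperation would not solve the problem, because that may be the failure-time scan.

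Then choose one of two analyses:

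- **Keep the categories.** Replace the t-test with an ordinal comparison of decreased / unchanged / increased, by Wilcoxon-Mann-Whitney or proportional odds.
- **Keep a mean.** Add one defined numeric ventricular measure to both the admission and the follow-up forms, read from scans already taken. Compare means, preferably adjusted for the pre-operative value; an unadjusted t-test on the change would also be valid. Record the modality, because ETV patients are to have MRI while shunt patients may have CT or MRI, so a measurement difference between modalities could appear as a difference between arms.

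The cost is a few form lines and a revised sentence in Statistical considerations. The numeric option adds a pre-operative field and a brief reading of existing images. Neither option needs an extra scan.
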